7.2 Descriptive Analysis

Using graphical methods and descriptive statistics, assumptions required for validity of statistical methods and presence of outliers will be assessed. Continuous variables will be summarized by means, standard deviations, interquartile ranges, and ranges. When appropriate, variables will be transformed to improve inferences. Categorical variables will be summarized by proportions.

7.3 Baseline Characteristics

Baseline characteristics of interest will be summarized by treatment groups to ensure balance due to randomization. The number of filter paper samples lost or not collected will also be tabulated by treatment groups and time points, as relevant, as well as PCR negative results or any other reason for excluding a sample from the analysis. In mixed infections, it is expected that sequencing will yield the genotype of the more prevalent strain(s), with sequencing error filters allowing detection of minor genotypes represented by as little as 1% of total reads and a minimum of 50 reads within a sample.

7.4 Handling Missed Vaccinations and Loss to Follow-Up

Analyses in the TVC are intention-to-treat, including all follow-up information after first vaccination regardless of number of vaccinations received, whereas analyses in the ATP cohort only include individuals who qualify for ATP cohort membership. For primary endpoint 1, the event of right-censoring is defined in Section 7.5.1.

7.5 Analyses of Primary Endpoint 1

The first primary endpoint is the time from a treatment-group-specific time origin until the time of the first molecular detection of a new malaria infection within a specified follow-up period.

VE will be assessed using a proportional hazards model, stratifying by study site in the study site-pooled analysis (i.e., allowing a separate baseline hazard rate of new malaria infection detection at each study site). For each vaccine group, VE (referred to as proportional hazards [PH] VE) is estimated as one minus the hazard ratio (vaccine/control vaccine) of the first molecularly confirmed infection detection with 95% Wald-based CI and a Wald test of the null hypothesis that VE equals zero. To minimize bias, it is helpful to control for predictors of molecular detection of new malaria infection (especially for the ATP analysis), and the Cox modeling analysis (implemented with the *coxph* function in the *survival* R package) will control for the baseline covariates listed in Section 6.2. The same proportional hazards modeling approach will be used for comparing the risk of molecular detection of new malaria infection between pairs of active vaccine arms, except hazard ratios will be assessed instead of VE parameters.

For the ATP analyses, differences in prognostic factors for molecular detection of new malaria infection could arise between the analyzed groups because the analyses are restricted to subgroups defined by the post-randomization variable of qualifying for the ATP cohort at Month 2.5 or Month 7.5 (Horne et al., 2001; Gilbert et al., 2013). In particular, a needed assumption for the ATP cohort analyses to assess causal effects of vaccination is that there are no unmeasured/unaccounted for baseline covariates that predict both ATP qualification status and the outcome type under study. Therefore, in preparation for the proportional hazard analyses, we will first study if there exist measured baseline covariates other than study site and ATP Propensity Score (described below) that are dual predictors of ATP status and either outcome type. If affirmative evidence is uncovered, such predictors will be adjusted for in every ATP cohort analysis, along with study site and ATP Propensity Score (if it is found to be predictive of the ATP status).

The following approach will be used to assess this evidence. Super Learner will be conducted to predict status of qualifying for the ATP from all available baseline covariates, using negative log-likelihood loss and 10-fold cross-validation. A simple parametric library of learners from the *SuperLearner* or *sL3* R packages will be used, for example, logistic regression that considers all possible two-way interactions from among the baseline covariates listed in Section 6.2 and that selects the best model based on stepwise model selection. If the classification accuracy is clearly greater than

expected from random noise, based on the 95% confidence interval for the cross-validated area under the ROC curve exceeding 0.5, then an ATP Propensity Score will be defined as the logit transformed Super Learner model fitted probabilities of being ATP, and all ATP cohort analyses of primary endpoint 1 will adjust for the ATP propensity score. The statistical analyses will use the nonparametric bootstrap for producing confidence intervals and p-values, to account for the fact that the propensity score is estimated. Depending on the number of variables that may be predictive of ATP qualification, we may consider more flexible methods for modeling the ATP propensity score, such as the highly adaptive lasso.

The TVC analyses directly compare hazard rates between vaccine arms not including control group data, as do the ATP analyses that compare vaccine arms within the same vaccination schedule (Month 0, 1, 2 or Month 0, 1, 7). In contrast, ATP analyses comparing vaccine arms with a Month 0, 1, 2 schedule, versus the Group 5 vaccine arm with a Month 0, 1, 7 schedule, include the control vaccine group data in each distinct follow-up period between vaccinations, to control for potential bias due to secular trends, for example caused by seasonality of malaria infection. In particular, the ATP analyses that make an adjustment via the control group are listed in Tables 2, 3 and 4 in Section 5.1.

For example, as in Table 2, the analyses are done using a Month 2.5 to 14 follow-up period for Groups 3 and 4 versus a Month 7.5 to 19 follow-up period for Group 5, creating the same amount of follow-up for malaria post-Dose 3 in the groups being compared.

We implement these analyses using the Cox proportional hazards model as follows: To assess relative VE comparing GP5 with GP2+GP3 in the ATP cohort during 11.5 months following the third dose in each regimen, we will fit (1) a Cox model to GP5 and GP1 data during months 7.5–19 of follow-up, and (2) a separate Cox model to GP2+GP3 and GP1 data during months 2.5–14 of follow-up. We will estimate the hazard ratio comparing GP5 months 7.5–19 with GP2+GP3 months 2.5–14 as the ratio of the estimated GP5-vs-GP1 hazard ratio in model (1) and the estimated GP2+GP3-vs-GP1 hazard ratio in model (2). We will use a nonparametric bootstrap procedure to construct a 95% CI for the GP5-vs-GP2+GP3 hazard ratio, as well as for obtaining a 2-sided p-value for the test of the null hypothesis that the hazard ratio equals one.

A secondary analysis will estimate instantaneous VE over time for each vaccine arm versus the control vaccine using nonparametric kernel smoothing (Gilbert et al., 2002). This analysis will provide pointwise and simultaneous 95% CIs about instantaneous VE over time, together with a p-value for whether instantaneous VE varies with time. Similarly, we will apply this method to estimate hazard ratios over time comparing pairs of vaccine arms. Nonparametric kernel smoothing will also be used to estimate the instantaneous risk of new malaria infection over time for each individual study arm, where this plot for the control vaccine arm is useful for displaying background malaria exposure and infection intensity over time.

For analyses of the TVC, the nonparametric kernel smoothing analysis described above will be applied to each of the pairwise study group contrasts described in Table 4, as well as for each individual study group in Table 4, all for follow-up between Month 0 and 20. For analyses of the ATP cohort, comparisons are done post-Dose 3 through 20 months, not including comparisons of Group 5 with Groups 3 and 4 because of the different times of dose 3. Specifically, Table 5 describes the ATP comparisons that are made, and the individual study group analyses will also be done. If for some of the study groups a substantial number of participants did not experience primary endpoint 1 by 20 months (operationally defined as at least 25% for at least one study group), then the nonparametric kernel smoothing analyses are repeated for follow-up through Month 32 (exactly as in Table 5 with M20 replaced with M32).

Table 5. Study Groups Compared and Individual Groups Analyzed by Nonparametric Kernel Smoothing of the Instantaneous Hazard Ratio (Primary Endpoint 1)

Analysis Type	Study Group and Follow-up Comparison
Assess Vaccine Efficacy (ATP)	GP2 M2.5-20 vs. GP1 M2.5-20
	GP3 M2.5-20 vs. GP1 M2.5-20
	GP4 M2.5-20 vs. GP1 M2.5-20
	GP5 M7.5-20 vs. GP1 M7.5-20
Assess Relative Vaccine Efficacy vs. Standard regimen R012-20 (ATP)	GP3 M2.5-20 vs. GP2 2.5-20
	GP4 M2.5-20 vs. GP2 2.5-20
Assess Relative Vaccine Efficacy (Other Comparisons) (ATP)	GP4 M2.5-20 vs. GP3 M2.5-20

An additional secondary analysis will estimate cumulative distributions of the time to the first molecular detection of a new malaria infection by study group. The cumulative distribution functions will be estimated in two ways: first, by using the Nelson-Aalen estimator for the cumulative hazard function, and second, by adjusting for other baseline participant characteristics via targeted maximum likelihood estimation (TMLE, Moore and van der Laan, 2009). The latter fully covariate-adjusted method is especially relevant for the ATP analysis, as described above. This analysis uses as an intermediate step an estimate of the distribution of the time to the first molecular detection of a new malaria infection conditional on baseline covariates (listed in Section 6.2), which is produced using the Super Learner method (as implemented in R packages *SuperLearner* or *s3*). Given the possibility of our requiring resampling methods (e.g., nonparametric bootstrapping) to obtain inference, we may restrict the Super Learner library of candidate regression methods to those that are computationally stable and run relatively quickly. For example, these candidate regressions will include regressions based on several different generalized linear models that include up to two-way interactions between covariates and treatment.

The estimated cumulative distribution functions of the time to the first molecular detection of a new malaria infection will be plotted with 95% pointwise and simultaneous

confidence intervals, through to the last time point in the specified time period. Similarly, point estimates and 95% confidence intervals will be produced for additive differences and cumulative incidence-based vaccine efficacy or cumulative relative risk contrasts between the two study groups being compared. These analyses will be done for each individual and pair of study groups specified in Table 5, analogously to the analysis of instantaneous kernel-smoothed hazard functions and their contrasts.

7.5.1 Handling of Loss to Follow-up for Primary Endpoint 1

Cox proportional hazards models and nonparametric inference on instantaneous hazard ratios over time

Regarding loss to follow-up, for both TVC and ATP cohort analyses, for each participant included in the analysis, the right-censoring time is defined as the last parasite negative sample collection date recorded during the follow-up period under study. The assumption of random censoring is needed for valid inferences.

The time to the first molecularly confirmed new malaria infection detection is right-censored. The analyses will be conducted using a standard right-censored failure time set-up, with failure time defined as the date of the first molecular detection of a new malaria infection.

TMLE inference on cumulative incidence curves and study group contrasts in cumulative incidence curves

Right-censoring/loss to follow-up is defined as for the proportional hazards analyses. The assumptions of random censoring after conditioning on measured baseline covariates and consistent estimation of the conditional distribution of the censoring time given these covariates is needed to assure valid inferences. Because the TMLE method is doubly-robust, it is valid even if the conditional censoring distribution is modeled inconsistently, as long as the conditional outcome regression is estimated consistently. The analysis will be done using the same time-to-event variable used for the Cox proportional hazards analysis.

7.6 Analyses of Primary Endpoint 2

Primary endpoint 2 is the number of new molecularly confirmed malaria infections during a specified follow-up period (see Section 7.6.1 for definition of an observed/known primary endpoint 2).

Plots of estimates of reverse cumulative distribution functions (rcdfs) of the number of new molecularly confirmed malaria infections by treatment arm occurring within each specified follow-up period will be used to summarize the distributions of primary endpoint 2. These plots show the proportion of participants with more than n new malaria infections on the y-axis versus n on the x-axis, and allow visual assessment of how specified quantiles differ over study groups (e.g., medians, 25th percentiles, 75th percentiles). The rcdfs will be estimated by targeted maximum likelihood estimation that

adjusts for the baseline covariates described in Section 6.2. Corresponding to these plots, the distribution of the total number of new malaria infections over specified time periods will be tabulated by study group. These analyses are done for each study group and follow-up period specified in Tables 2–4.

Vaccine efficacy against primary endpoint 2 for a given vaccine arm vs. the control arm will be assessed by the additive difference in the mean number of new molecularly confirmed malaria infections in each vaccine arm vs. the mean number of new molecularly confirmed malaria infections in the control vaccine arm. The targeted maximum likelihood estimator of Porter et al. (2011) will be used, which incorporates information in baseline study characteristics predictive of whether data are missing or predictive of the number of new molecularly confirmed malaria infections. This method also provides a way to estimate the variance of the estimated mean number of new molecularly confirmed malaria infections in each study arm. Based on these variance estimates, Wald tests will be used to test for the additive difference VE differing from zero and to obtain a 95% CI. These analyses are done for each comparison specified in Tables 2–4 with the control group as the comparison arm.

Similarly, the same methods will be used to test for differences in the mean numbers of new molecularly confirmed malaria infections between vaccine arms, and to compute 95% CI for these differences. Again Wald 95% CIs and Wald 2-sided p-values are used. These analyses are done for each comparison specified in Tables 2–4.

7.6.1 Handling of Loss to Follow-up and Missing Visit Data for Primary Endpoint 2

The number of new molecularly confirmed malaria infections must be estimated based on the genotyping/haplotyping data, and we use an operational definition for what data availability constitutes enough information for the study endpoint to be considered observed/known for an individual. A participant's endpoint is considered to be observed/known if both (a) s/he had at least one visit with genotyping data in the 75-day period leading up to the last scheduled visit in the given follow-up period (e.g., Month 0 to 20, Month 2.5 to 14, Month 7.5 to 19), and (b) s/he had genotyping data from at least 50% of scheduled visits during the given follow-up period. If the last scheduled visit in the given follow-up period was missed, then the 75-day period is keyed off of the target date of the missed visit. The premise for this estimator is that, with these available data, it will be possible to accurately estimate the number of new molecularly confirmed malaria infections during the follow-up period.

TMLE inference about reverse cumulative distribution functions (RCDFs)

The TMLE of the RCDF incorporates both a Super Learner estimate of the probability of missing the outcome conditional on baseline covariates and a Super Learner estimate of the outcome itself conditional on baseline covariates (again done with the *SuperLearner* or *sl3* R packages with default learners and baseline covariates described in Section 6.2). The method is well-suited to the application, because some participants who do not have an observed primary endpoint 2 due to not meeting condition (a) or (b) in the paragraph above will still have useful data (e.g., genotyping

results on, say, 40% of samples) for predicting primary endpoint 2, and any prediction ability even if quite imperfect improves efficiency of the analysis. More specifically, we view the objective of inference about the mean of primary endpoint 2 as a problem to address using two phases of data—phase one data measured in all participants and the phase two data the primary endpoint 2 (Y) that is missing for some participants. The phase one data include baseline characteristics of participants as well as auxiliary outcomes that may be predictive of the outcome Y of interest. Accounting for these phase one data, including information from participants with Y missing, can improve robustness and efficiency. We select as a phase one auxiliary outcome of interest (call it Y^*) the number of molecularly detected new infections divided by the number of available molecular detection tests during the time period of study for a given analysis. If a participant has zero in the denominator, then Y^* is set to 0. Moreover, the method is doubly-robust such that it gives valid inferences even if the Super Learner model for this prediction is inconsistent, as long as the probability of missing the outcome conditional on baseline covariates is consistently estimated. Thus, importantly, a completely accurate prediction is not required for valid inference, a property that has been shown theoretically and in simulation studies in many TMLE papers.

TMLE inference on mean number of new malaria infections and study group contrasts will be reported. Missing data for this TMLE are handled in the same way as described above for the TMLE of the RCDF.

7.7 Assessment and Comparison of Vaccine Efficacy after the Month 14 or 20 Boost through to Month 32

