Overall VE against the first new malaria infection (Primary Endpoint 1) and VE against genotype-specific new malaria infection (with genotype defined by full vaccine match, a mismatch, or a genetic distance) (Exploratory Endpoint 1) will be estimated using both cumulative incidence and hazard ratio methodologies, with multiple outputation [Follmann et al., 2003] to analyze data from complex infections, as in MALARIA-066.

*Primary Endpoint 2.* Plots of estimates of reverse cumulative distribution functions (rcdfs) of the number of new malaria infections by study arm will be used to summarize the distributions of the number of new infections. VE against all new infections for a given vaccine arm vs. the control arm will be assessed in two ways. First, VE will be analyzed by negative binomial regression allowing for interdependence between episodes within the same participant (non-linear mixed model with overdispersion parameter estimated from the random effect and follow-up time entered into the model as an offset) and adjusting for study site. Second, VE against all new infections will be assessed by the additive difference in the mean number of all new malaria infections in each vaccine arm vs. the mean number of all new malaria infections in the control vaccine arm.

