Longitudinal samples taken at Month 23, 26, 29, 32 are subjected to haplotyping in the same way as monthly samples drawn at monthly visits before and including Month 20.

To assess durability of VE, the primary endpoints are also analyzed (i) counting new molecularly confirmed malaria infections in the TVC cohort through 32 months after the first vaccination, and (ii) counting new molecularly confirmed malaria infections in the ATP cohort through 24 months post-Dose 3. Note that membership in the ATP cohort does not depend on whether Dose 4 is received.

The two primary endpoints assessed for durability for the ATP cohort analyses are:

1. Time from 14 days post-Dose 3 to molecular detection of the first new malaria infection through to 24 months after Dose 3
2. Number of new molecularly confirmed malaria infections during the same follow-up period used for the endpoint defined immediately above

The two primary endpoints assessed for durability for the TVC analyses are:

1. Time from first vaccination to molecular detection of the first new malaria infection through to the Month 32 study visit after first vaccination
2. Number of new molecularly confirmed malaria infections during the same follow-up period used for the endpoint specified immediately above

Table 4 summarizes the group comparisons and time periods for including new malaria infections using data through Month 32. Note that there is no scheduled Month 31 visit. Therefore, ATP cohort analyses listed in Table 4 that involve Group 5 will include new malaria infections detected in this group in the time period between 14 days post-Dose 3 and no later than the minimum of exactly 24 months post-Dose 3 and the time of completion of the Month 32 visit.

Table 4. Study Groups Compared to Assess Vaccine Efficacy or Relative Vaccine Efficacy Based on New Malaria Infection Endpoint Data Through Month 32 (Analysis of Primary Endpoints Longer Term)

Analysis Type	Study Group and Follow-up Comparison
Assess Vaccine Efficacy (TVC)	GP2 M0-32 vs. GP1 M0-32
	GP3 M0-32 vs. GP1 M0-32
	GP4 M0-32 vs. GP1 M0-32
	GP5 M0-32 vs. GP1 M0-32
Assess Vaccine Efficacy (ATP)	GP2 M2.5-26 vs. GP1 M2.5-26
	GP3 M2.5-26 vs. GP1 M2.5-26
	GP4 M2.5-26 vs. GP1 M2.5-26
	GP5 M7.5-31 vs. GP1 M7.5-31
Assess Relative Vaccine Efficacy vs. Standard regimen R012-20 (TVC)	GP3 M0-32 vs. GP2 M0-32
	GP4 M0-32 vs. GP2 M0-32
	GP5 M0-32 vs. GP2 M0-32
Assess Relative Vaccine Efficacy vs. Standard regimen R012-20 (ATP)	GP3 M2.5-26 vs. GP2 M2.5-26

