Setting $Z_i(t) = 1$ specifies an analysis of interest, in which case and $\gamma_k(u)$ is the log-scale increase in the intensity of having a new malaria infection of type k at time t and u unit time since the last new infection or vaccination. When and $\gamma_k(u)$ is positive, $\exp(\gamma_k(u))$ exceeds one and corresponds to a relative intensity (instantaneous relative risk) increasing with time since the last new infection or vaccination.

We can consider $U_i(t) = (U_{i1}^T(t), \dots, U_{iK}^T(t))^T$ as the part of the multi-type event history that could affect the intensity $\lambda_{ik}(t)$, where $U_{ik}(t)$ is related to the type- k event history of subject i . For example, choosing $U_{ik}(t) = (N_{ik}(t^-), t - T_{i,k,N_{ik}(t^-)})^T$ specifies the number of new infections molecularly detected between enrollment and time t (i.e., $N_{ik}(t^-)$ is the molecular force of infection mol[FOI] of strain k by time t for subject i) and the time since the last occurrence of molecularly detected strain k malaria infection, respectively. Specifying $\gamma_k(U_i(t)) = \eta_{kk}(t - T_{i,k,N_{ik}(t^-)})$ models time-varying effects since the last strain k infection, and specifying $\gamma_k(U_i(t)) = \eta_{kj}(t - T_{i,k,N_{ij}(t^-)})$ models how the time since the last strain j infection impacts time-varying effects on the intensity of strain k infection. In this notation $\eta_{kj}(t - T_{i,k,N_{ij}(t^-)})$ is a nonparametric function of $(t - T_{i,k,N_{ij}(t^-)})$.

The new infection event time variable is the same as used for the primary analyses, and the right-censoring time variable is modified. Specifically, the right-censoring time is defined as the last observed visit time (scheduled or unscheduled) before three consecutive missed scheduled visits with no intervening unscheduled visits. We selected three consecutive visits to define censoring based on a treatment-arm pooled descriptive analysis comparing several potential right-censoring definitions based on 2, 3, 4, 5, or 6 consecutive missed visits, where the percentage right-censoring was

45.3%, 29.5%, and 25.4% under the 2, 3, and 4 consecutive missed visits definitions of right-censoring, respectively.

To handle intermittent missed visits prior to right-censoring, we take advantage of the fact that the method flexibly allows subject-specific visit schedules.

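### Primary endpoint 2 has no overall ratio VE with a CI after an unexplained change from the protocol, and the 75-day 'known' rule does not fit the quarterly visits after Month 20

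*SAP*

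**What the plan says.** **Effect measure.** Protocol 6.1 gives two analyses of primary endpoint 2. The opening one is a rate model: "First, VE will be analyzed by negative binomial regression allowing for interdependence between episodes within the same participant", with follow-up time as the offset. The other is the additive difference in means. In SAP 7.6, VE on this endpoint "will be assessed by the additive difference in the mean number of new molecularly confirmed malaria infections in each vaccine arm" against control, estimated by TMLE with Wald tests and intervals. Reverse cumulative distribution plots and count tables are also planned. Neither SAP 7.6 nor the modification history mentions the negative binomial model.

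**When a count is observed.** SAP 7.6.1 sets two conditions: (a) "at least one visit with genotyping data in the 75-day period leading up to the last scheduled visit in the given follow-up period", and (b) "s/he had genotyping data from at least 50% of scheduled visits during the given follow-up period". A child who meets both contributes the raw count. A child who fails either is handled as missing by TMLE.

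**Longer follow-up.** SAP 7.7.2 applies the same methods to the Table 4 windows. After Month 20 the scheduled samples are sparser: "Longitudinal samples taken at Month 23, 26, 29, 32" (SAP 5.1.6).

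**Completeness reporting.** SAP 7.3 states: "The number of filter paper samples lost or not collected will also be tabulated by treatment groups and time points, as relevant". It does not ask for per-child completeness among children whose count is treated as observed.

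**The concern.** SAP 7.7.2 wants the results to show how VE on endpoint 2 changes from one follow-up segment to the next. An additive difference in counts cannot do that alone, because it rises with the length of the window even when relative protection is constant. It also depends on how many samples were obtained. TMLE deals with counts classed as missing; it does not rescale a count classed as known but built on half the samples. For endpoint 1, SAP 7.5 plans both additive differences and relative measures with intervals. Endpoint 2 lacks the relative one.

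The second issue is which children count as observed. Condition (a) is illustrated in SAP 7.6.1 only with windows whose visits are monthly. Carried to quarterly visits, it can class a nearly complete child as missing and a half-sampled child as known. The deciding factor can be an illness visit, which vaccination itself may affect.

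**Working it through.** **1. Visit grid.** SAP 5.2 expects about 31,500 monthly samples. With 1,500 children, 31,500 / 1,500 = 21 visits (Months 0 to 20), which agrees with the plan. Months 23, 26, 29 and 32 make 25 for M0-32. For M2.5-26 there are 18 (Months 3-20) + 2 = 20.

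**2. Window length.** Assume a constant infection rate, perfect counting and a vaccine/control rate ratio of 0.6. The difference is 0.4 x control rate x window length. Over the ATP windows of 6.5, 11.5 and 23.5 months the differences stand as 1 : 1.8 : 3.6 (11.5/6.5 and 23.5/6.5), while ratio VE is 40% in each.

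**3. How many visits are missed.** SAP 8.5.1 reports right-censoring of "45.3%, 29.5%, and 25.4% under the 2, 3, and 4 consecutive missed visits definitions of right-censoring, respectively", arms pooled. I read these as shares of children with at least one run of that length.
- Longest gap exactly 2: 45.3 - 29.5 = 15.8%. Exactly 3: 29.5 - 25.4 = 4.1%.
- Setting aside the 25.4% with 4 or more, among the other 74.6%: a run of 2 or more in 19.9/74.6 = 26.7%, and of 3 or more in 4.1/74.6 = 5.5%.
- With independent misses, the per-visit miss probability that reproduces these is 0.134 and 0.154 for 20 visits, or 0.122 and 0.143 for 24.

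So about 12-15% per visit. I use 13%. It could be higher, since gaps broken by an unscheduled visit are not counted.

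**4. Effect on the difference and the ratio.** I simulated the SAP counting rule (haplotype absent from the previous three samples) over visits M3-M14, with conditions (a) and (b) applied. The assumed inputs give 90 scenarios: control 0.8-10 infections/year, vaccine rate x0.6, mean duration 1-4 months, detection 85%, with and without clinically sampled infections, and 0, 3 or 5.76 further unscheduled samples/year.

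| Missed, equal in both arms | Share of difference kept | Largest move in ratio VE |
|---|---|---|
| 13% | 88-98% | 1 point |
| 30% | 75-95% | 2 points |
| Every child at 6 of 12 | 54-91% | 5 points |

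Full-sampling ratio VE is 33-41% against a true 40%, so the counting rule itself can attenuate the ratio. A second simulation with other assumptions (0.3 or 0.8 infections/month, rate ratio 0.7, 6,000 per arm, hence noisier) kept 86-98% at 10% missed and 66-79% at 40%, with the ratio of means shifting by about 0.03 at most.

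Unequal missingness (first simulation, 20% against 10%): if the vaccine arm misses more, 101-106% of the difference is kept and ratio VE rises 1-5 points. If control misses more, 68-94% is kept and ratio VE falls 1-7 points. Both scales are then biased.

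**5. Condition (a) on quarterly visits.** Spacing is 3 x 30.44 = 91.3 days. A 75-day window holds three scheduled visits in every monthly window and normally one in the Table 4 windows. The preceding visit enters only if it is at least 91.3 - 75 = 16.3 days late.
- M0-32: missing only Month 32 (24/25) is missing; 13/25 including Month 32 is known.
- M2.5-26: 19/20 without Month 26 is missing; 10/20 including it is known.

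Failure of (a) at 13% missed: monthly 0.13^3 = 0.22%; quarterly 13% before unscheduled samples. With unscheduled samples at 0.5/year (the control clinical incidence assumed in Protocol 6.2), 13% x exp(-0.5 x 75/365.25) = 11.7%. At 5.76/year (SAP 5.2: 8,640 / 1,500), 13% x exp(-5.76 x 75/365.25) = 4.0%.

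**6. Feasibility of a ratio CI.** SAP 7.6 says of its TMLE: "This method also provides a way to estimate the variance of the estimated mean number". Illustration with assumed means 2.5 and 1.6, SD 1.7 and 250 per arm: difference 0.90 (0.60-1.20). SE of the log ratio = sqrt[(1.7^2/250)(1/2.5^2 + 1/1.6^2)] = 0.080, so ratio VE is 36% (25-45%).

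**The case against.** Protocol 6.1 is a brief outline that defers to the SAP, and the retained difference is itself protocol-specified. That stands: the method may change. The history begins at version 1.0, so its silence does not show a late or data-driven removal. What is missing is the reason.

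The SAP is not without ratio-scale work on recurrent infections. Section 8.4.4 gives multiplicative VE estimates with intervals, and 8.5 models infection intensity in the TVC, allowing subject-specific visit schedules. That stands, but both are exploratory and 8.4.4 is haplotype-specific. Neither gives an overall ratio VE for the primary objective.

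A reader might infer that missed samples seriously distort the endpoint 2 result. The documents do not support that. At the inferred level the loss is modest and, with equal missingness, towards the null. The large losses belong to the sparsest sampling the rule admits, not to a likely arm mean. A reader might also infer that the negative binomial model must be restored. Its offset is follow-up time, which does not correct samples missed within follow-up.

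On condition (a), the windows ending by Month 20 are unaffected, and SAP 5.2 describes the later sampling as exploratory. SAP 7.6.1 uses the partial data of a child classed as missing, so that child is not discarded. Treating a count as missing when the last quarter is unsampled is also defensible. The rule's wording already keys M7.5-31 to Month 29, so no reference visit is lacking there. What remains is the inverted ordering of children, and that illness visits can decide status while the missingness model is stated as conditional on baseline covariates.

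**Conclusion.** The point holds as a reporting gap and a rule that does not fit its schedule, not as a threat to the validity of the primary windows. Primary endpoint 2 has no overall ratio VE with an interval under the primary objective, the protocol's model was dropped without explanation, and the remaining measure cannot by itself compare VE across windows of different length. The shrinkage from equal missingness is about 2-12% of the difference at 13% missed. That rests on my reading of the SAP 8.5.1 percentages, independent misses, and assumed infection rates, durations and detection; the documents give none of these by arm. In the Table 4 windows only, about 4-12% of children would fail condition (a) after unscheduled samples, against 0.2% in monthly windows, if the 13% also applies to the later visits.

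**What to change.** 1. In SAP 7.6, beside each vaccine-versus-control additive difference, report 1 minus the ratio of the TMLE means with a 95% CI, by the delta method from the planned arm-level variances. Present it as descriptive, with no p-value: Tables 2-4 hold 21 such comparisons, and the intervals should not serve as tests outside SAP 7.8. State why the negative binomial model was dropped; it need not return.
2. Extend the SAP 7.3 table to per-child sample completeness by arm among children with a known count. Rerun endpoint 2 at a stricter completeness threshold as a sensitivity analysis.
3. For windows ending after Month 20, define condition (a) on scheduled visits, with a window matched to quarterly spacing (about 105 days, for example). Keep the 75-day rule as a sensitivity analysis.

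The cost is SAP wording, one extended table and a few runs on existing data. Stricter thresholds lose precision, and a wider window can accept a child unsampled in the last quarter, which is why the 75-day result should stay. SAP 5.1.1.1 and 9.3 show that Month 20 data and VE results had already been seen by version 1.7, so any of these changes adopted after that analysis should be labelled post hoc.
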